4.4.3.10 Osteonecrosis

Osteonecrosis has been reported in subjects treated with cabozantinib. Additional risk factors include use of bisphosphonates and denosumab, chemotherapy and anti-angiogenic drugs, use of corticosteroids, local radiotherapy, and dental or orofacial surgery procedures.

Osteonecrosis of the jaw (ONJ) can manifest as jaw pain, osteomyelitis, osteitis, bone erosion, tooth or periodontal infection, toothache, gingival ulceration, or gingival erosion. Persistent pain or slow healing of the mouth or jaw after dental surgery may also be manifestations of osteonecrosis.

Perform an oral examination prior to initiation of cabozantinib and periodically during cabozantinib treatment. Advise subjects regarding oral hygiene practice and to quickly report symptoms to Investigator. Caution should be used in subjects receiving bisphosphonates.

Invasive dental procedures should be avoided. In cases where dental procedures are unavoidable, treatment with cabozantinib should be interrupted for at least 3 weeks prior to the procedure and resumed after complete wound healing has occurred. Bone healing may often require a protracted time.

Withhold CABOZANTINIB for development of ONJ until complete resolution.

4.4.3.11 Proteinuria

Proteinuria has been reported with cabozantinib. Proteinuria should be monitored by measuring UPCr. Table 0-6 provides treatment guidelines for proteinuria deemed related to cabozantinib.

Cabozantinib should be discontinued in subjects who develop nephrotic syndrome (proteinuria > 3.5 grams per day in combination with low blood protein levels, high cholesterol levels, high triglyceride levels, and edema).

Table 0-6: Management of Proteinuria Associated with Cabozantinib

Severity of Proteinuria (UPCR)	Management of Proteinuria
≤ 1 mg/mg (≤ 113.1 mg/mmol)	
 No change in cabozantinib treatment or monitoring
> 1 and < 3.5 mg/mg (> 113.1 and < 395.9 mg/mmol)	
 Consider confirming with a 24-h protein assessment within 7 days No change in cabozantinib treatment required if UPCR ≤ 2 mg/mg or urine protein ≤ 2 g/24 h on 24-h urine collection. Dose reduce or interrupt cabozantinib treatment if UPCR > 2 mg/mg on repeat UPCR testing or urine protein > 2 g/24 h on 24-h urine collection. Continue cabozantinib on a reduced dose if UPCR decreases to < 2 mg/mg. Consider interrupting cabozantinib treatment if UPCR remains > 2 mg/mg despite a dose reduction until UPCR decreases to < 2 mg/mg. Restart cabozantinib treatment at a reduced dose after a dose interruption. Repeat UPCR within 7 days and once per week. If UPCR < 1 mg/mg on 2 consecutive readings, UPCR monitoring can revert to protocol-specific times. (Second reading is confirmatory and can be done within 1 week of first reading.) If UPCR remains > 1 mg/mg and < 2 mg/mg for 1 month or is determined to be stable ($< 20\%$ change) for 1 month, check urine protein/creatinine per protocol or as clinically indicated.
≥ 3.5 mg/mg (≥ 395.9 mg/mmol)	
 Interrupt cabozantinib treatment pending repeat UPCR within 7 days and/or 24-h urine protein. If ≥ 3.5 mg/mg on repeat UPCR, continue to interrupt cabozantinib treatment and check UPCR every 7 days. If UPCR decreases to < 2 mg/mg, restart cabozantinib treatment at a reduced dose and monitoring of urine protein/creatinine should continue weekly until the UPCR decreases to < 1 mg/mg. If UPCR remains > 1 mg/mg and < 2 mg/mg for 1 month or is determined to be stable ($< 20\%$ change) for 1 month, check urine protein/creatinine per protocol or as clinically indicated.
Nephrotic syndrome	
 Discontinue cabozantinib treatment

4.4.3.12 Nervous System Disorders

Cabozantinib appears to represent minimal risk of adverse neurological effects based on nonclinical Good Laboratory Practice (GLP)-compliant toxicology studies. Dysphonia, dysgeusia, headache, dizziness, confusional state, convulsion, depression, memory impairment, hypoesthesia, peripheral neuropathy, insomnia, ataxia, and encephalopathy have been observed in clinical studies with cabozantinib. The development of any new or progressive, unexplained neurological symptoms should be assessed for underlying causes.

RPLS has been reported. RPLS should be considered in any subject presenting with seizures, headache, visual disturbances, confusion or altered mental function. Cabozantinib treatment should be discontinued in subjects with RPLS.

4.4.3.13 Hepatocellular Toxicity

Investigators should monitor for DILI diligently and report any potential events. Elevation of aminotransferases (ALT and AST) and bilirubin have been observed during treatment with cabozantinib. It is recommended that subjects with elevations of ALT, AST, and/or bilirubin have more frequent laboratory monitoring of these parameters. If possible, hepatotoxic concomitant medications should be discontinued in subjects who develop increased values of ALT, AST, or bilirubin, and other potential causes for these increases (e.g., cancer-related, infection) should be evaluated. See Table 0-7 for management of hepatocellular toxicity.

Table 0-7 Management of Hepatocellular Toxicity Associated with Cabozantinib

Event – Elevation of ALT, AST, or Total Bilirubin (CTCAE v4)	Management

Grade 1
 
ALT or AST > ULN – 3.0 x ULN
 
Bilirubin > ULN – 1.5 x ULN
	
 • Dose adjustment is usually not required. • Consider discontinuing concomitant hepatotoxic medications and add supportive care as indicated.

Grade 2^{a,b}
 
ALT or AST > 3.0 – 5.0 x ULN
 
Bilirubin > 1.5 – 3.0 x ULN
	
 • Interrupt cabozantinib if lasting longer than 1 week and consider more frequent monitoring of ALT, AST, and bilirubin. • Restart cabozantinib after lab abnormalities have resolved to at least CTCAE Grade ≤ 1 or baseline.

Grade 3^{a,b}
 
ALT or AST > 5.0 – 20.0 x ULN
 
Bilirubin > 3.0 – 10.0 x ULN
	
 • Interrupt cabozantinib and consider more frequent monitoring of ALT, AST, and bilirubin. • Restart cabozantinib at a reduced dose after lab abnormalities have resolved to at least CTCAE Grade ≤ 1 or baseline. • Discontinue if lab abnormalities cannot be reversed despite interruption of study treatment.

Grade 4^b
 
ALT or AST > 20.0 x ULN
 
Bilirubin > 10 x ULN
	
Subjects should have cabozantinib interrupted immediately. Discontinue cabozantinib unless the following criteria are met:
 
 • Subject is deriving clear clinical benefit as determined by the Investigator, and approved by the Principal Investigator. • Toxicity can be managed with a dose reduction following recovery to Grade 1 (or baseline) and optimal medical care.

^aElevations of aminotransferases when hepatic metastases are present may not require dose modifications if there is less than a doubling in the aminotransferases from baseline and if there are no progressive elevations in serum bilirubin concentration or coagulation factors.
 
^bThe following condition requires discontinuation of cabozantinib: Drug-related ALT or AST >3 × ULN in combination with total bilirubin >2 x ULN without other reasonable explanation, consistent with drug-induced liver injury (DILI).
	

4.4.3.14 Infections and Infestations

Infections are commonly observed in cancer subjects. Predisposing risk factor include a decreased immune status (e.g., after myelosuppressive anticancer therapies, splenectomy), destructive growth of the underlying malignancy including bone marrow infiltration with suppression of normal hematopoiesis, as well as the presence of IV devices.

Infections and abscesses should be treated with appropriate local care and systemic therapy. Cabozantinib should be interrupted until complete healing has taken place.

4.4.3.15 Blood and Lymphatic System Disorders

Hematological toxicities (i.e., neutropenia and thrombocytopenia) and associated complications have been observed after administration of cabozantinib and may be managed with dose interruptions and/or dose reductions. Subjects with hematologic toxicities may require additional or more frequent laboratory tests according to institutional guidelines.

Dose reductions or dose interruptions for hematological toxicities are not mandated but can be applied as clinically indicated. Supportive care for thrombocytopenia or anemia, such as transfusions, may be managed according to institutional guidelines. The use of colony-stimulating growth factors should be considered. Febrile neutropenia or evidence of infection associated with neutropenia must be assessed immediately and treated appropriately and in a timely manner according to institutional guidelines.

4.4.3.16 Fatigue

Common causes of fatigue, such as anemia, deconditioning, emotional distress (depression and/or anxiety), poor nutrition, dehydration, sleep disturbance, and hypothyroidism should be ruled out and treated according to standard of care.

Pharmacological management should be considered after disease specific morbidities have been excluded when not prohibited.

4.4.3.17 Weight Loss

Anorexia and weight loss should be managed according to local standard of care including nutritional support. Pharmacologic therapy should be considered for appetite enhancement when not prohibited by a particular protocol.

4.4.3.18 Corrected QT Prolongation

The effect of orally administered cabozantinib 140 mg qd on QTc interval was evaluated in a placebo-controlled study in subjects with MTC. A mean increase in QTcF of 10-15 ms was observed after 4 weeks after initiating cabozantinib treatment. A concentration-QTc relationship could not be definitively established. Changes in cardiac wave form morphology or new rhythms were not observed. No cabozantinib-treated subjects in this study had a QTcF > 500 ms. Review of the larger safety database (~5000 subjects exposed to cabozantinib in clinical trials and in post-marketing experience) confirmed the absence of safety concerns associated with QT prolongation. There were no events of torsades de pointes reported. Concomitant treatment with strong cytochrome P450 (CYP) 3A4 inhibitors, which may increase cabozantinib plasma concentrations, should be avoided. If at any time on study there is an increase in QTcF to an absolute value > 500 ms, two additional ECGs must be performed with intervals not less than 3 min apart within 30 min after the initial ECG.

If the average QTcF from the three ECGs is > 500 ms, the following actions must be taken:

- Interrupt cabozantinib treatment
- Hospitalize symptomatic subjects (e.g., with palpitations, dizziness, syncope, orthostatic hypotension, a significant ventricular arrhythmia on ECG) for a thorough cardiology evaluation and management
- Consider cardiology consultation for asymptomatic subjects for evaluation and management
- Check electrolytes, especially magnesium, potassium and calcium; correct abnormalities as clinically indicated

- Check concomitant medications for any medication that may have contributed to QT prolongation, and if possible, discontinue these medications (<http://www.qtdrugs.org>)
- Repeat ECG triplicates hourly until the average QTcF is ≤ 500 msec, or otherwise determined by consultation with a cardiologist or appropriate expert.
- Subjects with QTc prolongation and symptoms must be monitored closely until the QTc elevation and symptoms have resolved. Cabozantinib treatment may be restarted at a reduced dose level if all of the following conditions are met:
 - Symptoms are determined to be unrelated to the QT interval prolongation
 - The QTcF value > 500 ms is not confirmed
 - Cabozantinib treatment has been interrupted through a minimum of 1 week following the return of the QTcF to ≤ 500 ms.
- QT prolongation can be unequivocally associated with an event other than cabozantinib administration and is treatable/has been resolved
- Following reinitiation of study treatment, ECGs must be repeated weekly for 2 weeks, then every 2 weeks for 1 month, then according to the protocol-defined time points.
- Cabozantinib treatment must be permanently discontinued if either of the following applies:
 - Cardiac evaluation confirms that symptoms are the consequence of QT interval prolongation
- Recurrence of QTcF prolongation after reinitiation of study treatment at a reduced dose

4.4.3.19 Electrolyte Disorders

Serum electrolyte disorders including hyponatremia, hypokalemia, hypomagnesemia, and hypophosphatemia have been reported during treatment with cabozantinib, and serum electrolyte levels should be monitored frequently while receiving cabozantinib. Clinically relevant electrolyte disorders should be managed according to the dose modification guidelines as outlined in [Section 4.4](#) or as clinically indicated. Standard clinical practice guidelines should be used for management of electrolyte disorders and may include oral or intravenous replacement.

4.4.3.20 Endocrine Disorders

Thyroid dysfunction, primarily hypothyroidism, has been observed with cabozantinib treatment. The underlying potential mechanism of thyroid dysfunction observed with cabozantinib treatment remains unclear. Management of thyroid dysfunction (e.g., symptomatic hypothyroidism) should follow accepted clinical practice guidelines.

4.4.3.21 Angioedema

Angioedema should be managed according to standard practice. The subject should be observed until symptoms resolve, with particular attention to maintaining an open airway.

4.4.3.22 Musculoskeletal and Connective Tissue Disorders

Cabozantinib appears to represent minimal risk of adverse musculoskeletal effects based on nonclinical GLP-compliant toxicology studies. The development of new or progressive, unexplained musculoskeletal symptoms such as pain or weakness should be assessed for underlying causes. Rhabdomyolysis has been reported. Cabozantinib should be discontinued in subjects with serious and life-threatening rhabdomyolysis and interrupted if less severe forms occur when there are no other clear causes. Reinitiation of cabozantinib treatment must be discussed with and

approved by the sponsor. Therapy of rhabdomyolysis should include supportive care and standard medical intervention.

4.4.3.23 Respiratory, Thoracic and Mediastinal Disorders

Dyspnea has been reported in clinical studies with cabozantinib. Symptoms should be managed according to locally accepted clinical practice including an assessment for underlying causes. Pulmonary embolism should be considered as possible causes for new onset dyspnea given the risk of thrombosis associated with inhibition of VEGF signaling. Furthermore, fistula formation (Section 6.2.2) and pneumonia have been reported in subjects treated with cabozantinib and should be considered as clinically indicated in subjects presenting with pulmonary symptoms.

4.4.3.24 COVID-19

If a diagnosis of COVID-19 is confirmed on study, the disease should be managed as per local or institutional guidelines. The overall risk-benefit ratio for the subject should be evaluated to determine whether holding study treatment(s) is in the best interest of the subject. More specific guidance regarding COVID-19 is included in the study protocols.

4.4.4 Management of Temozolomide Related Adverse Events

The most common adverse reactions ($\geq 10\%$ incidence) are: alopecia, fatigue, nausea, vomiting, headache, constipation, anorexia, convulsions, rash, hemiparesis, diarrhea, asthenia, fever, dizziness, coordination abnormal, viral infection, amnesia, and insomnia.

The most common Grade 3 to 4 hematologic laboratory abnormalities ($\geq 10\%$ incidence) that have developed during treatment with temozolomide are: lymphopenia, thrombocytopenia, neutropenia, and leukopenia.

Allergic reactions have also been reported.

Please refer to [Appendix A](#) for dose modification algorithms for potential combination treatment related adverse events.

Table 0-8: Temozolomide Dosing Interruption or Discontinuation during Treatment Period

Toxicity	Temozolomide Interruption	Temozolomide Discontinuation	Reduce Temozolomide by 1 Dose Level
Absolute Neutrophil Count (ANC)	≥ 0.5 and $< 1.5 \times 10^9/L$	$< 0.5 \times 10^9/L$	≥ 0.5 and $< 1.0 \times 10^9/L$
Platelet Count	≥ 10 and $< 100 \times 10^9/L$	$< 10 \times 10^9/L$	≥ 10 and $< 50 \times 10^9/L$
NCI-CTCAE non-hematological toxicity (except for alopecia, nausea and vomiting)	Grade 2	Grade 3 or 4	Grade 3

Treatment with temozolomide may be continued when all of the following conditions are met:

- $ANC \geq 1.5 \times 10^9/L$
- Platelet count $\geq 100 \times 10^9/L$
- NCI-CTCAE non-hematological toxicity \leq Grade 1 (except for alopecia, nausea and vomiting)

Table 0-9: Temozolomide Dose Levels

Dose 0 (Assigned Starting Dose)	Dose Level 1	Dose Level 0	Dose Level -1
150 mg/m ² /day	200 mg/m ² /day	150 mg/m ² /day	100 mg/m ² /day

Please see [Appendix B](#) for Daily Dose Calculations by Body Surface Area (BSA).

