40. Schiff, D., et al., Phase 1 dose escalation trial of the safety and pharmacokinetics of cabozantinib concurrent with temozolomide and radiotherapy or temozolomide after radiotherapy in newly diagnosed patients with high-grade gliomas. *Cancer*, 2016. 122(4): p. 582-7.
doi:10.1097/CAD.000000000000108

APPENDIX A - DOSE MODIFICATION ALGORITHMS FOR POTENTIAL COMBINATION TREATMENT RELATED ADVERSE EVENTS

AE Terms & Descriptions	Dose Modification Algorithms
Diarrhea	
a. Grade 1-2 (duration < 48 hr)	a. Continue Cabozantinib at the current dose. If it does not improve with supportive measures consider a dose reduction. Continue temozolomide at the current dose.
b. Intolerable Grade 2 or Grade 3	b. Interrupt Cabozantinib and temozolomide until Grade ≤ 1 then consider restarting Cabozantinib at reduced dose. Dose reduce temozolomide by one dose level for Grade 3 only. Discontinue temozolomide for grade 4.
	c. Refer to the Table 0-3 for the management of diarrhea.
Neutropenia	
a. Neutrophil count <1.5	a. Interrupt temozolomide and cabozantinib until neutrophil count $\geq 1.5 \times 10^9/L$.
b. Neutrophil count <1.0	b. Interrupt temozolomide and cabozantinib until $\geq 1.5 \times 10^9/L$. Reduce temozolomide by 1 dose level. Continue cabozantinib at the same.
c. Neutrophil count <0.5	c. Discontinue temozolomide, interrupt cabozantinib until neutrophil count is $\geq 1.5 \times 10^9/L$ then resume at same dose.
Febrile Neutropenia	
Grade 3 or 4	Interrupt temozolomide and cabozantinib until resolved. Upon resumption, reduce temozolomide by 1 dose level. Continue cabozantinib at the same dose.
Thrombocytopenia	
Grade 1 or 2	Interrupt temozolomide until $\geq 100 \times 10^9/L$. Continue cabozantinib.

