Grade 2	
 • Cabozantinib treatment may be continued if PPES is tolerated. • Cabozantinib should be dose reduced or interrupted if PPES is intolerable. • Continue urea 20% cream twice daily AND high potency steroid cream (e.g., clobetasol 0.05%) once daily and add analgesics (e.g., NSAIDs/gamma-aminobutyric acid agonists) for pain control if needed. 
Reassess at least weekly; if PPES worsens or affects self-care, proceed to the intervention guidelines for Grade 3.
 
 • Continue temozolomide at the investigator's discretion
Grade 3	
 • Interrupt cabozantinib treatment until severity decreases to Grade 1 or 0. • Continue treatment of skin reaction with high potency steroid cream (e.g., clobetasol 0.05%) twice daily AND analgesics. • Resume study drug at a reduced dose if PPES recovers to Grade ≤ 1. • Discontinue subject from study treatment if PPES does not improve within 6 weeks • Interrupt/continue temozolomide at the investigator's discretion
Proteinuria (UPCR)	
≤ 1 mg/mg (≤ 113.1 mg/mmol)	
 • No change in cabozantinib or temozolomide treatment
> 1 and < 3.5 mg/mg (> 113.1 and < 395.9 mg/mmol)	
 • Refer to Table 0-6 for the management of cabozantinib treatment. No change in temozolomide treatment
≥ 3.5 mg/mg (≥ 395.9 mg/mmol)	
 • Refer to Table 0-6 for the management of cabozantinib treatment. No change in temozolomide treatment.
Nephrotic syndrome	
 • Discontinue cabozantinib
Hepatocellular Toxicity	
Grade 2 AST or ALT or Total Bili lasting longer than a week	
 • Interrupt cabozantinib and temozolomide until Grade 1. • Refer to the Section 4.4.3.13 for the management of DILI
Other Treatment Related Adverse Events (such as fatigue, nausea, vomiting, anorexia, weight loss, etc)	

Grade 1 or Grade 2 (tolerable)	
 • Add supportive care as indicated. • Continue cabozantinib and temozolomide treatment at the current dose; monitor as clinically indicated

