Intolerable Grade 2 or Grade 3	
 • Interrupt cabozantinib and temozolomide treatment until it is a Grade 1 or tolerable grade 2. Restart both cabozantinib and temozolomide at the current dose or dose reduced by one level.^b For Grade 3 AEs related to Temozolomide dose reduce by one level. • *Note: It is recommended that dose holds be as brief as possible
Grade 4-related to temozolomide Grade 4-related to cabozantinib (except clinically non-relevant laboratory abnormalities)	
 • Discontinue temozolomide. • Subjects should have cabozantinib interrupted immediately. • Discontinue cabozantinib unless the following criteria are met: Subject is deriving clear clinical benefit as determined by the investigator Toxicity can be managed with a dose reduction following recovery to Grade 1 (or baseline) and optimal medical care
Study treatment dose adjustment is only needed if the toxicity was deemed related to cabozantinib treatment or had an unclear relationship to cabozantinib treatment. ^b except nausea, vomiting, and alopecia- no dose interruption required for temozolomide	

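### Table 0-8 assigns Grade 3 non-hematological toxicity to both stopping and reducing temozolomide, and Section 4.4.3.5 bars factor Xa inhibitors that Section 4.5.1 allows for DVT

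*Combined protocol and SAP*

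**What the plan says.** **Temozolomide.** Table 0-8 in Section 4.4.4 has three action columns, in the order interruption, discontinuation, reduction by one level. Its last row is "NCI-CTCAE non-hematological toxicity (except for alopecia, nausea and vomiting) Grade 2 Grade 3 or 4 Grade 3". Read across, Grade 2 interrupts, Grade 3 or 4 discontinues, and Grade 3 reduces.

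Appendix A gives combination-specific instructions. For diarrhea: "Dose reduce temozolomide by one dose level for Grade 3 only. Discontinue temozolomide for grade 4". In its block for other treatment-related events: "For Grade 3 AEs related to Temozolomide dose reduce by one level", with discontinuation at Grade 4 related to temozolomide. Appendix A is not uniform. For blood pressure at or above 160/110 and for Grade 3 hand-foot syndrome the text is "Interrupt/continue temozolomide at the" investigator's discretion. The hepatocellular entry is keyed to "Grade 2 AST or ALT or Total Bili lasting longer than a week". A closing note reads: "Study treatment dose adjustment is only needed if the toxicity was deemed related to cabozantinib treatment or had an unclear relationship to cabozantinib treatment".

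Sections 4.4 and 4.4.4 both refer the reader to Appendix A. Neither says that it overrides Table 0-8.

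**Anticoagulation.** Section 4.4.3.5 prefers low molecular weight heparin for thrombotic events and rules out oral anticoagulants, with direct factor Xa inhibitors among its examples and no exception. Section 4.5.1 allows rivaroxaban, edoxaban or apixaban after the first dose, with treatment of DVT as the example. It then sends the reader to 4.4.3.5 for management of clots and to 4.5.2 for the prohibited anticoagulants. Section 4.5.2 prohibits only betrixaban in that class. Exclusion 9 opens with a general ban, but 9c excepts the three named drugs under stated conditions.

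**The concern.** Each conflict gives a site two instructions that cannot both be followed.

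In the first, the choice is between permanent loss of one of the two study drugs and a step down of one dose level. Sites that resolve it differently would give different amounts of temozolomide before the 12-week assessment that carries the primary endpoint.

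In the second, an investigator who treats an on-study DVT with one of the three named drugs complies with 4.5.1 and departs from the letter of 4.4.3.5. These are matters of safety and consistent conduct.

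**Working it through.** **1. Is the Table 0-8 overlap a feature of the table or a fault in one row?**

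| Row | Interrupt | Discontinue | Reduce |
|---|---|---|---|
| ANC (×10⁹/L) | 0.5 to <1.5 | <0.5 | 0.5 to <1.0 |
| Platelets (×10⁹/L) | 10 to <100 | <10 | 10 to <50 |
| Non-hematological | Grade 2 | Grade 3 or 4 | Grade 3 |

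In the first two rows, the discontinue range never meets the reduce range, and the reduce range lies inside the interrupt range. The third row fails both tests: Grade 3 is in discontinue and in reduce, and is absent from interrupt. All cells are present and in the same order as the rows above, so a text-extraction fault is unlikely.

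**2. Dose consequence of the two readings.**

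Inputs: the planned doses are 150 mg/m² in Cycle 1 and 200 mg/m² from Cycle 2, on Days 1-5 (Sections 4.2 and 4.3). The levels in Table 0-9 are 200, 150 and 100 mg/m². The 12-week scan is at C4D1 (Section 5.0, note b), so Cycles 1-3 precede it.

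Assumptions: the event occurs after Day 5, so that cycle's course is complete. It resolves by the next Day 1. A reduced dose is then held. There is no other delay or toxicity.

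Plan: 5×150 + 5×200 + 5×200 = 750 + 1000 + 1000 = 2750 mg/m².

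Event in Cycle 1 (one level down from 150 is 100):
- Discontinue: 750 + 0 + 0 = 750; 750/2750 = 27%.
- Reduce: 750 + 5×100 + 5×100 = 1750; 1750/2750 = 64%.

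Event in Cycle 2 (one level down from 200 is 150):
- Discontinue: 750 + 1000 + 0 = 1750; 64%.
- Reduce: 750 + 1000 + 5×150 = 2500; 2500/2750 = 91%.

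The readings differ by 1000 mg/m² in the first case and 750 mg/m² in the second.

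**3. Anticoagulation, section by section.**

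| Place | Rivaroxaban, edoxaban, apixaban |
|---|---|
| Exclusion 9c | Allowed, with conditions |
| 4.5.1, after first dose | Allowed if clinically indicated, DVT as example |
| 4.5.2 | Not among the prohibited drugs; only betrixaban is named in the class |
| 4.4.3.5 | Class barred, no exception |

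Three places agree, and 4.4.3.5 is the outlier. No arithmetic applies.

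**The case against.** The intent can be read. Appendix A is cited just above Table 0-8, and its block for other treatment-related events is a catch-all that reduces at Grade 3 and discontinues at Grade 4. For anticoagulants, 4.5.1 names 4.5.2 as the place for prohibited drugs, so a reader who follows the cross-references reaches one answer. Both arguments have force, and they show which way to correct the text. They do not remove the conflict: no sentence gives Appendix A precedence over Table 0-8, and 4.4.3.5, the section on managing clots, still says no.

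Some stronger readings are tempting but not supported:

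- *That a subject with a Grade 3 event could return to 100% of planned dose because escalation to 200 mg/m² depends on counts alone.* Sections 4.2 and 8.2 describe the planned step up from the starting dose, and Table 0-8 is the specific rule for toxicity. The lack of a temozolomide re-escalation rule is a gap, not an instruction to restore full dose.
- *That Table 0-8 alone decides temozolomide at Grade 3 hepatic toxicity.* The hepatocellular entry has no Grade 3 temozolomide instruction, but the catch-all block may cover it.
- *That the Appendix A closing note cancels temozolomide adjustments.* It repeats a cabozantinib footnote of Table 0-2 and may have lost its marker in conversion. It needs a stated scope, and no more should be read into it.
- *That the safety lead-in rule is affected.* It counts subjects who have to stop therapy in the first cycle. The plan does not say whether losing temozolomide alone counts, so I claim no effect.

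**Conclusion.** Both passages are wrong as written. The non-hematological row of Table 0-8 places Grade 3 in two incompatible columns and omits it from a third. Section 4.4.3.5 lacks an exception that the three other relevant places contain.

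For a single affected subject, the choice of reading moves Cycle 1-3 temozolomide from 27% to 64% of plan (Cycle 1 event) or from 64% to 91% (Cycle 2 event), under the assumptions listed above. The anticoagulant conflict arises only when one of the three named drugs is chosen over the preferred heparin.

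The documents give no frequency for either situation, so no trial-level effect can be sized. A reader might infer that the two-stage design is compromised. It is not: its error rates do not depend on either passage. Both items should be corrected for safety and consistent conduct.

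Two neighbouring points are secondary and for the investigators to settle. One is the missing temozolomide re-escalation rule. The other is tolerable Grade 2 toxicity. Table 0-8 interrupts at Grade 2 and resumes at Grade 1 or lower. Appendix A says "Continue cabozantinib and temozolomide treatment at the current dose; monitor as clinically indicated" for tolerable Grade 2, and after an intolerable Grade 2 or a Grade 3 event "Interrupt cabozantinib and temozolomide treatment until it is a Grade 1 or tolerable grade 2".

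**What to change.** **Table 0-8, non-hematological row.** Set interruption to Grade 2 or 3 and discontinuation to Grade 4, and keep reduction at Grade 3. The row then matches Appendix A and the nesting of the rows above it. Because this settles Grade 3 on the less conservative action, it needs clinical confirmation first.

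**Precedence.** Add one sentence to Section 4.4.4: where Appendix A and Table 0-8 differ, Appendix A governs, including its block for other treatment-related events. This would also settle tolerable Grade 2 in favour of Appendix A, so the investigators should confirm that they want that result before the sentence is adopted.

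**Appendix A closing note.** State that it applies to cabozantinib adjustments only.

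**Section 4.4.3.5.** Except rivaroxaban, edoxaban and apixaban from the ban, keep low molecular weight heparin as preferred, and cross-refer to 4.5.1 and 4.5.2.

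The cost is amendment wording and a memo to sites. Sample size, visits and analysis do not change.
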